#### 7. ASSESSMENTS

Every effort should be made to ensure that the protocol required tests and procedures are completed as described. However it is anticipated that from time to time there may be circumstances, outside of the control of the investigator that may make it unfeasible to perform the test. In these cases the investigator will take all steps necessary to ensure the safety and well-being of the subject. When a protocol-required test cannot be performed the investigator will document the reason for this and any corrective and preventive actions which he/she has taken to ensure that normal processes are adhered to as soon as possible. The study team will be informed of these incidents in a timely fashion.

### 7.1. Analgesic Effect Assessments

### 7.1.1. Pain Intensity

Daily average NRS-Pain scores will be assessed with an 11-point NRS ranging from zero (no pain) to 10 (worst possible pain) captured on the diary (Appendix 7). A subject will rate their average pain intensity during the past 24 hours by choosing the appropriate number from 0 to 10 as shown below. The subject will conduct the self-assessment daily with the caregiver(s) in the evening prior to bedtime and recorded in the diary during the Treatment and Post-Treatment Periods. These diary assessments will be reviewed by the investigator at the in-clinic visits for the purpose of assessing the need for titrating study drug and will not be documented. Pain Intensity will also be completed at the in-clinic visits during the Treatment and Post-Treatment Periods. Only the in-clinic visit pain assessments will be documented for analysis.

Select the number that best describes your average pain in the past 24 hours. (Select one number only).

0	1	2	3	4	5	6	7	8	9	10
No										Worst
Pain										Possible Pain

#### 7.1.2. Rescue Medication Use

The use of Rescue Medication will be recorded in the diary during the Treatment and Post-Treatment Periods.

The administration of acetaminophen and/or NSAID's administered during the study is recorded by the caregiver(s), but is not to be more than required by label and at the direction of the investigator.

### 7.2. Safety Assessments

#### 7.2.1. Adverse Events

### 7.2.1.1. Recording of Adverse Events by Investigator

The investigator is responsible for the detection and documentation of all events meeting the definition of an AE or serious adverse event (SAE). All AEs and SAEs will be recorded in the source documents. All AEs will be entered on the appropriate CRF page from the time of dosing until completion of the End of Study requirements. All SAEs will be recorded on the CRF from the time written informed consent is given until 28 days after the last dose of study drug is administered. Information collected will include the nature of the event, as well as its date and time of onset, intensity, duration, causality, and outcome. Even if the investigator regards the AE as not reasonably attributable to study drug, the event must be recorded in the source documentation including the CRF.

# 7.2.1.2. Recording of Adverse Events Using a Home Diary

The study caregiver (parent or legal guardian) will be instructed on the use of a diary, which the caregiver will record dosing information, concomitant medications, and AEs between visits to the clinic. The caregiver will be instructed on the signs and symptoms of opioid overexposure (eg, toxicity), opioid withdrawal, as well as other signs and symptoms commonly associated with opioid AEs (eg, nausea, headache, constipation).

The Clinical Site will contact the caregiver (ie, at least on a weekly basis) to ensure that the caregiver is monitoring for opioid AEs and is recording all relevant AE information in the home diary. All AEs will be brought to the attention of the investigator.

### 7.2.2. Vital Signs

Vital signs, including resting systolic and diastolic blood pressure, pulse, and respiratory rate, are performed at designated study visits as outlined in the Schedule of Activities.

### 7.2.3. Clinical Laboratory Tests

The hematology, clinical chemistry, and urinalysis tests presented in Table 1 are performed at designated study visits as outlined in the Schedule of Activities.

#### **Table 1. Clinical Laboratory Tests**

#### Serum Chemistry

Alanine aminotransferase (ALT; serum glutamate Chloride

pyruvate transaminase)

Albumin

Alkaline phosphatase

Aspartate aminotransferase (AST; serum glutamic

oxaloacetic transaminase)

Bicarbonate Bilirubin (total) Blood urea nitrogen

Calcium

Serum creatinine Creatine phosphokinase

Glucose

Phosphorus Potassium Protein (total) Sodium

#### **Serum Chemistry**

Cholesterol (total)

Hematology

Hematocrit Red blood cell count Hemoglobin White blood cell count

Platelet count White blood cell differential count (lymphocytes, monocytes, neutrophils, eosinophils, and basophils)

Other

Routine urinalysis (dip-stick unless otherwise indicated)

# 7.2.4. Electrocardiogram

A single, 12-lead ECG will be performed at Screening for determination of ECG-related eligibility. The ECG should be recorded after subjects have been resting at least 5 minutes in the supine position in a quiet environment. An abnormal, clinically significant finding at screen will be cause to not enroll the subject. Post-Screening ECGs may be collected if needed (for-cause), at the discretion of the investigator. In the event a clinically significant ECG abnormality is observed on a for-cause ECG, the investigator should consider evaluation of the subject by a cardiologist.

### 7.2.5. Clinical Opiate Withdrawal Scale (COWS)

Clinical opiate withdrawal is assessed by a clinician-administered instrument, the COWS, at designated study visits as outlined in the Schedule of Activities.

The COWS (Appendix 8) contains 11 common opiate withdrawal signs or symptoms rated by the clinician. The summed score of the 11 items is used to assess a subject's level of opiate withdrawal.

A subject experiencing a COWS score ≥13 is treated for opiate withdrawal signs and symptoms according to the investigator's medical judgment.

### 7.2.6. Physical Examination

A physical examination is performed at designated study visits as outlined in the Schedule of Activities. Physical examinations may be conducted by a physician, trained physician's assistant, or nurse practitioner as acceptable according to local regulation. A complete physical examination will include head, ears, eyes, nose, mouth, skin, heart and lung examinations, lymph nodes, gastrointestinal, musculoskeletal, and neurological systems.

For measuring weight, a scale with appropriate range and resolution is used and must be placed on a stable, flat surface. Subjects must remove shoes, bulky layers of clothing, and jackets so that only light clothing remains. They must also remove the contents of their pockets and remain still during measurement of weight.

Height and weight is measured only at Visit 1 of the Screening Period.

### 7.2.7. Urine Drug Test

A urine drug sample is collected at Screening, as outlined in the Schedule of Activities, for the purpose of mainly detecting illicit drug substances. Certain positive test results may be acceptable providing documentation is confirmed by the investigator. An opioid finding at the Screening visit is an expected result due to a subject's standard of care therapy not being discontinued at Screen or washed out by the Baseline visit. Illicit drugs found during these tests will disqualify the subject from entering the study.

Specifically, the following drugs will be screened for by immunoassay by a central laboratory:

- Opioids ( ie, codeine, morphine, hydrocodone, hydromorphone, dihydromorphone, oxycodone);
- Amphetamines (including methamphetamine and ecstasy);
- Phencyclidine;
- Cocaine;
- Tetrahydrocannabinol (marijuana);
- Methadone.

#### 7.3. Pregnancy Testing

For female subjects of childbearing potential, a serum pregnancy test, with sensitivity of at least 25 mIU/mL, will be performed at the Screening and Visit 6/ET, and a urine pregnancy test, with sensitivity of at least 25 mIU/mL, will be performed at all other study visits (ie, Visits 2-5), including unscheduled visits. A negative pregnancy result is required before the subject may receive the study drug. Pregnancy tests will also be done whenever one menstrual cycle is missed during the treatment period (or when potential pregnancy is otherwise suspected) and at the end of the study to confirm the subject has not become pregnant during the study. In the case of a positive human chorionic gonadotropin test, the subject will be withdrawn from study medication but may remain in the study. Pregnancy tests may also be repeated as per request of IRB/Ethics Committees (EC) or if required by local regulations.

#### 7.4. Assessment of Suicidal Ideation and Behavior

### 7.4.1. Columbia- Suicide Severity Rating Scale (C-SSRS)

Suicide ideation and behaviors will be evaluated at all scheduled visits from Screening (Visit 1) through End of Study (Visit 7). The age-appropriate scale must be utilized based upon the subject's age at the Screen (Visit 1) visit.

For subjects who will be ages 7-11:

• The Children's Lifetime/Recent (Version 6/23/10) (Appendix 3) of the C-SSRS should be completed at the Screening Visit (Visit 1). Please note the Lifetime/Recent scale refers to the subject's lifetime experience. At all study visits following the Screening Visit, the Children's Since Last Visit (Version 6/23/10) (Appendix 5) of the C-SSRS should be utilized, even if the child has their 12th birthday during the study. The Since Last Visit version refers to the subject's experience since their last visit.

For subjects who will be ages 12-17:

• The Baseline/Screening (Version 1/14/09) (Appendix 4) of the C-SSRS should be completed at the Screening Visit (Visit 1). Please note the Screening scale refers to the subject's lifetime experience. At all study visits following Visit 1, the Since Last Visit (Version 1/14/09) (Appendix 6) of the C-SSRS should be utilized. The Since Last Visit version refers to the subject's experience since their last visit.

At screening, if the subject endorses a 4 or 5 on the C-SSRS ideation section or reports any suicidal behavior, then the subject is not eligible for study participation and an evaluation of suicide risk (risk assessment) must be completed. Refer to Section 7, Assessments for details on Risk Assessment.

At every on-site study visit after screening, if the subject endorses a 4 or 5 on the C-SSRS ideation section or reports any suicidal behavior, then the subject must be discontinued as outlined in Section 6.5, Subject Withdrawal and an evaluation of suicide risk (risk assessment) must be completed. Refer to Section 7, Assessments for details on Risk Assessment.

**Risk Assessment**: In the event that a subject endorses a 4 or 5 on the C-SSRS ideation section or reports any suicidal behavior, an evaluation of suicide risk (risk assessment) completed as part of the psychiatric evaluation and assessment of subject safety to participate will be done by the following child and adolescent mental health provider (MHP): In the United States: 1) Child and Adolescent Psychiatrists (board certified or board eligible), 2) psychiatrists who have training and experience in the diagnosis and treatment of psychiatric disorders in the pediatric population, or 3) Psy.D. or Ph.D. level Clinical Psychologists, licensed Master's level Clinical Social Workers (MSW), or licensed psychiatric Nurse Practitioners (PNP) who have training and experience in the diagnosis and treatment of psychiatric disorders in the pediatric population.

Written documentation of the risk assessment should be included in the subject's source documentation, and the risk assessment CRF will be completed. The risk assessment CRF serves as further verification that the psychiatric evaluation and assessment of subject safety has been completed for all subjects endorsing items 4 or 5 on the C-SSRS ideation section or reporting any suicidal behavior. Note: Per protocol, subjects endorsing items 4 or 5 on the C-SSRS ideation section or reporting suicidal behavior at screening are ineligible for study

participation. Subjects endorsing items 4 or 5 on the C-SSRS ideation section or reporting any suicidal behavior following the Screening visit must be withdrawn from the study and will receive the appropriate medical care. Refer to Section 6.5, Subject Withdrawal.

#### 7.5. Pharmacokinetic Evaluation

### 7.5.1. Blood Sample Collection and Handling

During Visit 4, a total of two 6 mL ( $2\times6$  mL) PK samples of blood will be taken at least two hours apart for the purpose of quantifying the concentrations of morphine, M3G, M6G, naltrexone, and  $6-\beta$ -naltrexol in plasma. PK samples will be collected at Visit 6 or at Early Termination if they are not collected at Visit 4. The clock time of the first PK sample will be documented (and noted relative to the clock time of the morning dose of PF-06412528) on the CRF. The second PK sample will be drawn at least 2-hours after the first sample and the clock time recorded. Note: The exact dosing date and time for the previous 3 doses are also to be recorded on the appropriate CRF.

Plasma samples received by the bioanalytical laboratory will be assayed for either morphine and morphine metabolites (MG3, MG6) or naltrexone and 6-β-naltrexol using a validated analytical method that conforms with Pfizer's standard operating procedures. All samples collected during the study will be assayed and retained in accordance with local regulations and, if not used (or reused) within this timeframe, will be destroyed. Please refer to the central laboratory procedures manual for collection and storage information.

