#### Pharmacokinetic Assessments

Once the subjects have achieved a stable dose of PF-06412528, two blood samples will be taken at two time points post-dose at least two hours apart during Visit 4 to characterize the PK of morphine and its metabolites and determine the exposure levels of naltrexone and 6-\beta-naltrexol.

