#### 9.3.3. Pharmacokinetic Analysis

Given the expected very low fluctuation in steady-state morphine concentrations following PF-06412528 BID dosing in children based on PF-06412528 study ALO-KNT-202 in adults, the concentrations observed during the maintenance phase will be used as an estimate of  $C_{ss,av}$  of morphine and its metabolites (data permitting) in pediatric subjects. The CL/F of morphine will be estimated using a ratio of the daily dosing rate of PF-06412528 and the estimates of morphine  $C_{ss,av}$  in the Maintenance Phase. The concentration-time dataset will be analyzed to obtain estimates for Vz/F of morphine in pediatric subjects, data permitting. Covariates of interest (PF-06412528 dosage, age, body weight, gender, concomitant medications etc) will be assessed for their ability to account for the observed variability in morphine  $C_{ss,av}$ .

The observational data will be summarized using descriptive statistics (mean, standard deviation, median, minimum, and maximum) for the study group as a whole. Data permitting, graphical representations and regression analyses may be used to characterize the dose-exposure relationships for morphine, naltrexone, and 6-β-naltrexol.

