Blood samples will be collected for pharmacokinetic analysis at Visit 4 only for those subjects that achieve a stable dose between Visits 3a-d. Two blood samples will be taken two-hours apart at Visit 4. Subjects will be assigned 1:1 with respect to beginning the pharmacokinetic sampling within either 0-to-5 hours or >5 to \leq 9 hours after the morning dose of PF-06412528. Only the first of the two pharmacokinetic samples must be collected within the designated time window; the other sample should be collected approximately two hours after the first sample.

The purpose of the Post-Treatment Period (Visit 7) is to perform safety assessments 7 \pm 2 days after the last dose of PF-06412528. All treated subjects will be required to attend Visit 7, including those who discontinued early.

The purpose of the End of Study Period (Visit 8) is to perform final safety assessments 28 \pm 2 days after the last dose of PF-06412528 for all treated subjects. This visit may be performed as an in-clinic visit or by telephone.

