3. INTERIM ANALYSES, FINAL ANALYSES AND UNBLINDING

No interim analysis is planned. Final analysis will follow the official database release. Since this is an open label single-arm study, unblinding is not applicable.

With respect to pharmacokinetics, it is estimated that a sample size of N=50 per treatment group would provide adequate (>80%) power to estimate CL/F and Vd/F, taking into consideration the sample size estimates for various levels of PK variability as described by Wang, et al. However, since the study is expected to enroll slowly over time, modeling and simulation will be performed - beginning with adult population PK model and adding pediatric data from each age group as it becomes available – to verify that the sample size and the sampling scheme proposed for the present study are adequate to estimate CL/F and Vd/F with 80% power to establish the 95% CI within 60 to 140% of the geometric mean value for each PK parameter.

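### The SAP assigns children 1:1 to early and late PK sampling windows but the protocol gives sites none, so coverage of the dosing interval is not assured and the flat-profile premise behind Css,av and CL/F may be only partly checkable

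*Protocol*

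**What the plan says.** **SAP 2.1 (Study Design).** "Subjects will be assigned 1:1 with respect to beginning the pharmacokinetic sampling within either 0-to-5 hours or" a later window of >5 to 9 h after the morning dose. The window binds one draw only: "Only the first of the two pharmacokinetic samples must be collected within the designated time window". The second draw is to follow with a gap of about 2 h.

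**SAP 3.** Modelling and simulation are planned "to verify that the sample size and the sampling scheme proposed for the present study are adequate" for CL/F and Vd/F.

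**Protocol.** The Summary states that "two blood samples will be taken at two time points post-dose at least two hours apart during Visit 4". Section 7.5.1 adds: "The second PK sample will be drawn at least 2-hours after the first sample and the clock time recorded". Schedule of Activities footnote 12, section 3.2.2 and section 6.2.2 (Visit 4) give the same minimum gap. Visit 6/Early Termination asks only that the times of two samples be recorded. None of these places gives a post-dose window or an assignment.

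**Use of the samples.** Protocol 9.3.3 begins "Given the expected very low fluctuation in steady-state morphine concentrations following PF-06412528 BID dosing in children", citing an adult study. It then takes Maintenance concentrations as Css,av and computes CL/F as daily dosing rate divided by Css,av. Both are primary PK endpoints (2.2.1). SAP 6.2.1.1 instead names CL/F and Vd/F as primary, and SAP 7.3 and 8.2.2 estimate them with a NONMEM model on actual sampling times.

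**The concern.** A site that draws every child at 1 h and 3 h complies fully with the protocol. So does one that draws every child at 6 h and 8 h. Under 9.3.3 either set is read as Css,av. If the profile is not flat, CL/F carries an error that depends on clinic routine. It tends to run in the same direction in every child sampled at similar times, so a larger sample does not shrink it.

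The flat-profile premise is carried over from adults on BID dosing. Protocol 1.3 gives reasons to test it in children, by age: a mean half-life of 2.3 h in the cited paediatric study, and apparent clearance about 1.7 times higher in the younger group. Testing it needs samples from different parts of the interval, which the SAP scheme would supply and the protocol does not require. The simulations in SAP 3 would also be judging a scheme that sites have not been told to follow.

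**Working it through.** **1. The plan's own figure.** SAP 3 states that N=50 per group gives >80% power for a 95% CI within 60-140% of the geometric mean. No between-subject CV is given, so the figure cannot be reproduced as a point value. With a log-normal parameter, power = P(t(0.975, n-1)·s/√n ≤ ln 1.4), where s is the sample SD on the log scale. For n=50 this is at least 99.9% at CV 100%, 83% at CV 150%, and falls to 80% at about CV 153%. The claim is plausible. It concerns random error only and says nothing about a shift from sampling time.

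**2. Model for the shift.** One compartment with first-order absorption and elimination (the SAP's starting model), at steady state, with t = time since dose minus lag, taken within the interval:

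C(t)/Css,av = [ka·k·τ/(ka-k)] × [e^(-kt)/(1-e^(-kτ)) - e^(-ka·t)/(1-e^(-ka·τ))]

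Error in CL/F = 1/(mean C/Css,av) - 1.

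Inputs:
- τ = 12 h (BID).
- k = ln 2/2.3 = 0.301 /h, from the half-life in Protocol 1.3.
- ka and lag are **assumptions**; the documents give neither. Protocol 5.4 puts approximate steady state at 24 to 36 h. Reading that as 90% at 36 h gives ln 10/36 = 0.064 /h; as 95% at 24 h it gives ln 20/24, about 0.124 /h. Lag is ranged over 0-2 h. ka = 0.03 /h stands for a nearly flat profile.

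**3. Results** (mean C/Css,av, with the CL/F error in brackets):

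| ka, lag | all at 1+3 h | all at 6+8 h | even split |
|---|---|---|---|
| 0.03, 0 h | 1.01 (-1.1%) | 1.02 (-2.0%) | 1.02 (-1.5%) |
| 0.03, 2 h | 0.96 (+4.4%) | 1.04 (-4.2%) | 1.00 (-0.1%) |
| 0.064, 0 h | 1.03 (-2.9%) | 1.04 (-3.6%) | 1.03 (-3.3%) |
| 0.064, 2 h | 0.91 (+9.4%) | 1.09 (-8.4%) | 1.00 (-0.3%) |
| 0.124, 0 h | 1.08 (-7.5%) | 1.05 (-4.9%) | 1.07 (-6.2%) |
| 0.124, 2 h | 0.85 (+17.4%) | 1.17 (-14.4%) | 1.01 (-1.0%) |

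A second calculation used the paediatric CL/F and volume in Protocol 1.3 (23.1 mL/min/kg and 5.2 L/kg, half-life 2.6 h) and no lag. With all first samples at 2-4 h and the second 2 h later, the CL/F error is -4%, -9%, -14% and -29% at ka 0.03, 0.08, 0.12 and 0.35 /h (peak-trough fluctuation 13%, 33%, 48% and 115%). Under the SAP windows it is -1%, -3%, -4% and -8%.

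**4. How far the recorded pairs reveal a problem.** For ka 0.064-0.124 /h and lag 0-2 h:
- Pairs at 1 and 3 h: C(3)/C(1) = 1.12 to 1.69, which is visible.
- Pairs at 6 and 8 h: C(8)/C(6) = 0.87 to 0.97, a weaker signal. In the worst late case (CL/F -14.4%) it is 0.93.
- Pairs straddling the peak can look flat. At ka 0.124 /h with no lag, the 3 h and 5 h values are 1.20 and 1.18 of Css,av: ratio 0.98, CL/F error -16%.

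**5. QD children.** Total daily doses of 10 and 15 mg are given once daily (Protocol 5.3.1, 5.4). The SAP windows end at about 9 + 2 = 11 h after dose, so 11-24 h goes unsampled. With τ = 24 h and ka 0.064-0.124 /h, the even split averages 1.04 to 1.45 of Css,av, a CL/F error of 1/1.04 - 1 = -4% to 1/1.45 - 1 = -31%.

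**The case against.** A reader might infer that the flat-profile premise cannot be checked at all. The documents do not support that. Both draw times, the morning dose and the previous three doses are recorded (Protocol 6.2.2, 7.5.1), and each child contributes a timed pair. A 1 h and 3 h pair would show a rise under the model above. What is lost is assured coverage: other pairs are far less informative.

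A reader might also infer that the SAP's analysis depends on the windows. It does not. No SAP analysis uses the assignment; the model takes actual times and may borrow adult profiles or fix the absorption parameters. The Css,av method belongs to the protocol alone. On the SAP side, the exposure is the adequacy check in SAP 3 and the volume estimate.

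The SAP also appears to predate Amendment 2: it keeps a Visit 8, chronic pain as the indication, and Vd/F as primary. Aligning the SAP to the protocol is therefore a legitimate remedy. This explains the mismatch but does not remove it.

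The size of the shift is open to challenge. It rests on ka and lag values that the documents do not give, and it implies more fluctuation than the protocol expects. Protocol 1.3 also says the half-life is considerably longer after a controlled-release oral product. Perfect clustering across many sites, with morning doses encouraged over a four-hour span, is an extreme. All of this stands, and the percentages should be read accordingly.

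Finally, a central laboratory manual is cited for collection details, and some PK text is redacted. Neither could be seen. Nothing visible says that either assigns windows.

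**Conclusion.** The conflict is real and bears on a primary endpoint. The SAP describes, and plans to verify, a sampling scheme that the protocol does not instruct sites to follow, while Protocol 9.3.3 treats concentrations as interchangeable over the interval. Coverage is not assured, so the premise may be only partly checkable in children.

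The CL/F shift of about -14% to +17% is an illustration for two fully clustered BID schedules under assumed ka 0.064-0.124 /h, lag 0-2 h and half-life 2.3 h. It should not be read as a forecast. An even split reduces it to about 0 to -6%, and at ka 0.03 /h clustering costs only about 4%. If fluctuation is as low as the protocol expects, the effect is small; the gap is that the protocol does not ensure data to show it. For QD children the windows are not a remedy. The change should be made, because missing sampling times cannot be recovered later.

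**What to change.** 1. **Reconcile** SAP 2.1 and SAP 3 with Protocol 7.5.1, 6.2.2 (Visit 4) and Schedule footnote 12, including the gap (about 2 h in one, at least 2 h in the other). Preferably carry the 1:1 windows into the protocol, assigned within each age group through the IRT system already in place for drug supply. Otherwise delete them from the SAP and redo the adequacy check for unrestricted sampling times.
2. **In either case, pre-specify a flatness check** in 9.3.3 and the SAP, to be done before concentrations are used as Css,av: dose-normalised concentration against recorded time since dose, and the within-child ratio of sample 2 to sample 1, both by age group.
3. **Analyse QD children separately.** The low-fluctuation premise is stated for BID, and the windows do not span 24 h.

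Cost: wording in two documents and an assignment flag in the IRT, with no extra blood or visits. The downside of the windows is a longer or later clinic stay for families assigned the late one. Deleting them instead costs a repeat of the simulations and leaves coverage to chance. The flatness check uses data already collected.
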